6.5 Implementation evaluation

After the index patient completes their participation in the study, the study team may reach out to invite them to complete a survey or qualitative interview to determine implementation outcomes. Since this is a pilot study, we will also reach out to participants who have withdrawn from the trial in order to determine why they chose not to complete the behavioral trial. Questions in the implementation evaluation will include whether the patients found the timing of the intervention to be feasible or appropriate, whether they found the intervention to be helpful, how they felt about including network members in their recovery process, etc.

6.5 Data Collection Schedule

Time point	Individual Counseling Arm	Social Network Arm
Baseline (Week 0)	
Written consentPERSNETDemographics and stroke data (Age, Sex, Stroke severity, Charlston comorbidity index)Blood pressure measure under direct observation	
Written consentPERSNETDemographics and stroke data (Age, Sex, Stroke severity, Charlston comorbidity index)Blood pressure measure under direct observationNetwork members contact info
Session 1 (Week 2 (+/- 7 days))	
BP measure under direct observationFeasibility measures: number of participants, time of session, connection problems.	
BP measure under direct observationFeasibility measures: number of participants, time of session, connection problems.
Session 2 (Week 6 (+/- 7 days))	
BP measure under direct observationFeasibility measures: number of participants, time of session, connection problems.	
BP measure under direct observationFeasibility measures: number of participants, time of session, connection problems.
End line (Week 12 (+/- 7 days))	
BP measure under direct observationPERSNETPROMISFeasibility measures: number of participants, time of session, connection problems.	
BP measure under direct observationPERSNETPROMISCaregiver burden (primary caregiver)Intervention process evaluation (qualitative semi-structured interview)Feasibility measures: number of participants, time of session, connection problems.
Upon completion of study (or after withdrawal)	
Implementation survey or qualitative interview	
Implementation survey or qualitative interview

6.6 Participant Remuneration

Patient-subjects will be remunerated for participation in the study. We plan to recruit 60 patients (30 intervention arm, 30 control arm), and all participation will be voluntary. Patients will receive \$25 for completion of the first study session, \$25 for completion of the second study session, and \$50 upon completion of the final study session. Patient-subjects will receive this in the form of a single payment upon completion of study participation. Patient-subjects will also be able to keep the blood pressure cuff provided at the beginning of the study.

Network-subjects will not receive any remuneration for participation in the study.

7. Risks and Discomforts

The study team believes there is no more than minimal risk involved to the patient subjects for all phases of the research, as all medical decisions are ultimately made by their treating provider, and the study will follow best practices for maintaining confidentiality of study subjects involved. This study will also not interfere with the ordinary workings of clinical practices. All analyses and data provided to the study investigators will be based on anonymized, untraceable coded identifiers; this encryption eliminates the risk associated with an unlikely breach of confidentiality.

The main potential risk is a breach of confidentiality of the patient and their network members. Texting over mobile/cell phones carries security risks because text messages to mobile/cell phones are not encrypted. We are minimizing this risk by only transmitting mostly stroke prevention and hypertension control information, task adherence, and social skill education. Breach of this information should have minimal consequences, but the patient and network members will be informed of this risk during the consent process.

Protections Against Risk

To protect against the risk of inappropriate disclosure of personal health information, the investigators at BWH will only access study data with encrypted identifiers. As described, all members of the research team have completed or will complete appropriate human subjects research training and patient privacy training related to the Health Insurance Portability and Accountability Act (HIPAA). The study team has a history of collaborative evaluations with delivery organizations that involves transfer of the minimum data necessary to complete rigorous evaluations, involving the use of encrypted identifiers to ensure patient confidentiality.

To protect against risk associated with the use of a tablet device and SMS communication, the designated study-specific cellular device will undergo all provisions and configurations required by MGB Enterprise Mobility Management (EMM) and the Research Information Security Office (RISO).

To ensure the confidentiality and security of all data, the research team operates a secure, state-of-the-art computing facility housed at Mass General Brigham Healthcare's data center. The MGB data center is a secure facility that houses both computing environments as well as clinical systems and electronic medical records for several large hospitals in Eastern Massachusetts. Entry into the computer room requires staffed computer room security. The Division's computers are connected to the MGB networking backbone with 10 gigabit-per-second fiber links. Network security is overseen by electronic medical records systems to the research team's data. All data are transmitted to programmers' workstations in an encrypted state. Backups are created using 256-bit AES encryption, the current Department of Defense standard for data security, and are stored in a locked facility. The redundancy,

extensive data power, and security of the computer facility confirm the capacity to collect and manage data and ensure confidentiality for all project participants.

Any identifiable information will be safeguarded from the providers in accordance with IRB practices, limit access to any information in accordance with IRB practices, limit access to the information to study investigators actively involved in the research who have all undergone human subjects research training and destroy any recordings from the qualitative interviews upon completion of the research.

8. Benefits

Social network interventions may help increase treatment adherence for patients with uncontrolled hypertension after stroke. Thus, the research could have both immediate benefits for subjects enrolled in the study as well as for the larger populations of patients with poorly controlled hypertension. Several deliverables for this work will also be produced for the public, researchers, and policymakers, which will be shared as generalized knowledge. These deliverables include the results from the study, implementation toolkits, and the responsiveness profile characteristics.

9. Statistical Analysis

9.1 Statistical Hypothesis

The null hypothesis is that rates of systolic blood pressure change at 3 months will be equal in the intervention arm when compared to the control.

9.2 Power analysis

This pilot trial will be conducted for 12 months. In that time frame, the study team expects 1126 patients to be eligible across Brigham and Women's Hospital, Massachusetts General Hospital and Spaulding Rehabilitation Hospital (85% of all 1325 ischemic stroke patients given broad inclusion criteria). It is expected that ~20% of the patients will agree to participate based on prior experience of recruitment in this population. This creates a pool of 225 or 19 per month. Thus, the study team can feasibly recruit 60 patients within 4-5 months with buffer for unexpected issues.

Assuming a mean blood pressure of 150 +/- 13 points in the individual counselling arm and an alpha of 0.05, this study will need to enroll a total of 54 patients (i.e., 27 per arm) to have 80% power to detect a 10 mm Hg reduction blood pressure from the social network intervention. Therefore, planned enrollment of 60 should be sufficient power for this study to allow for loss to follow-up.

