5.1 PATIENT SUBJECT ENROLLMENT

The study staff will perform daily screening of hospital admissions based on the study’s inclusion and exclusion criteria listed above. If an inpatient meets criteria, the study staff will directly approach the nurse, physician attending, or physician assistant who is caring for the patient to briefly explain the study and determine an appropriate time to meet with the patient. We will verify the inclusion and exclusion criteria with the treating provider. If permission is granted by the treating provider, the study staff will meet with the patient at bedside, explain the study to the patient, and ask the remaining exclusion criteria to confirm their eligibility. In particular, the study staff will confirm that the patient has a phone and is capable of sending and receiving text messages. Study staff will also ensure that patients are willing to engage network members in the study if assigned to the intervention arm. If the patient is interested in participating in the study, the study staff will then obtain informed consent from the patient using MGB-approved REDCap digital signature consent process, conduct baseline surveys, randomize the patient and, for intervention arm participants, collect contact information for their network members who will be directly contacted and invited to participate. Patients will be stratified according to network size (<5 vs 5 or more) and location of hospitalization (MGH or BWH), and then be randomized using a 1:1 ratio to receive individual hypertension counseling or the social network intervention.

Patients who are eligible for participation in this study and two other IRB approved studies led by [name] ([name], 2020P003739 and 2020P000320) may be approached for participation in both studies within one enrollment visit. Study staff will explain both studies and emphasize that patients can choose to only participate in one of the studies. If interested, patients will be provided consent forms for both studies and will agree to participate in each study separately. Patients will then go through baseline questionnaires for both studies, completing any repeated questionnaires between both studies only once. Participation in the three studies will otherwise be separate.

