6. STUDY PROCEDURES

6.1 Consent/Enrollment and Baseline Visit

The study staff will meet with the eligible patients at bedside, explain the study to the patient, and obtain written informed consent using MGB-approved REDCap digital signature consent process. The consent form will include consent for enrolled participants to receive follow-up outreach after

completion of the trial to participate in an implementation evaluation, to include either a brief survey or a brief qualitative interview. Study staff will then help the patient complete baseline questionnaires consisting of the validated PERSNET social networks questionnaire, stroke information, and the CES-D depression screen. Additional covariates, such as medication use, will be retrieved from the EHR. The PERSNET resulting network map will be used to identify network team members. Participants will then be randomized to either the Social Networks (intervention) arm or the Individual Counseling (control) arm. In the Individual Counseling arm, while the patient's network will be mapped, it will not be acted upon. In the Social Network arm, network members identified will be invited to participate in the study per the enrollment description above (Section 5.2). All patients will be provided with a wide-range blood pressure cuff (Medline MDS4001 blood pressure monitor) and instructions for weekly home monitoring. Patient will be asked to use this cuff to collect a baseline blood pressure measurement at the time of enrollment. A blood pressure measurement will also be collected from the patient's EHR on the day of discharge from the hospital. Finally, patients will be offered several Zoom meeting options and will schedule the first counseling session with study staff based on their availability.

Both this study and protocols 2020P003739 and 2020P000320 ask patients to complete the PERSNET social networks questionnaire. To simplify the enrollment process, patients that have consented to participate in both studies will only be asked to complete these questionnaires once for protocol 2022P000444. Data from these questionnaires will then be shared with protocols 2020P003739 and 2020P000320.

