9.3 Statistical analysis

The primary outcome will be absolute reduction in systolic blood pressure at 3 months. Secondary outcomes will be attainment of a post-stroke hypertension treatment goal of <130/80 and patient-reported physical function (based on the NIH PROMIS physical function sub-scale). These outcomes will be evaluated, for intervention and control patients, on a 10-minute Zoom exit interview with direct observation on video by the study nurse.

Analysis will be conducted using intention-to-treat principles. Evaluation of the primary outcome and physical function secondary outcome will be completed using linear controlling for any differences in baseline variables despite randomization. Logistic regression will be used for attainment of post-stroke hypertension treatment goal of <130/80 controlling for any differences in baseline variables.

For Aim 2, we will assess how a subset of questions in PERSNET predict the set of network members who were engaged in the intervention. We will calculate positive predictive value of the subset questions versus full network survey questions.

10. Monitoring and Quality Assurance

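### The 80% power in section 9.2 is not tied to the primary analysis: the trial is sized on a blood pressure level, while 9.3 analyses SBP reduction with covariates chosen by observed baseline differences

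*Combined protocol and SAP*

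**What the plan says.** - **Sample size (9.2).** The planning assumption reads "Assuming a mean blood pressure of 150 +/- 13 points in the individual counselling arm and an alpha of 0.05". With 80% power for a 10 mm Hg effect this leads to 54 patients, 27 per arm; 60 are to be enrolled to cover loss to follow-up. The section does not call 13 an SD, say which time point 150 and 13 describe, give a source, or state the sidedness of alpha.
- **Hypothesis (9.1).** The null is that "rates of systolic blood pressure change at 3 months will be equal in the intervention arm when compared to the control".
- **Outcome and model (9.3).** "The primary outcome will be absolute reduction in systolic blood pressure at 3 months". It is analysed by a linear method "controlling for any differences in baseline variables despite randomization". No covariate is named.
- **Stratification (5.1).** Randomization is 1:1, stratified by network size (under 5, or 5 and more) and hospital (MGH or BWH). Section 9.3 does not mention these factors.
- **Baseline reading (6.1 and the Data Collection Schedule).** At enrollment, "Patient will be asked to use this cuff to collect a baseline blood pressure measurement at the time of enrollment". The schedule lists at week 0 a "Blood pressure measure under direct observation". Section 6.1 also takes a reading from the health record on the day of discharge. Section 9.3 does not say which reading the reduction is measured from.

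**The concern.** Two gaps meet here.

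First, the covariates in the primary model depend on the data. Adjusting for whatever differs between arms means that baseline SBP, probably the most useful covariate for an SBP outcome, enters only if the arms happen to be imbalanced on it, by a criterion that is not stated. The stratification factors are in the same position. The analyst would settle the primary model after seeing the data.

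Second, the power statement uses the spread of a level. The variance of a change score depends on the SDs at both times and on rho; the residual variance of a baseline-adjusted model depends on the week-12 SD and rho. The plan gives neither an SD of change nor rho. The same 54 patients could therefore give well under or well over 80% power, depending on an analysis choice that the plan leaves open.

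**Working it through.** **Inputs from the plan:** difference 10 mm Hg, 13 read as an SD, alpha 0.05, power 80%, 1:1 allocation, 27 per arm (54), 60 enrolled.

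**Step 1. Reproduce 54.** n per arm = 2(z_alpha + z_power)² × SD² / difference².
- Two-sided: 2 × (1.960 + 0.842)² × 13² / 10² = 26.53, so 27 per arm and 54 in total. This matches.
- One-sided: 20.90, so 21 per arm. This does not match.

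So the figure is an unadjusted two-group comparison with SD 13 and two-sided alpha. Power at 27 per arm is 80.7% by the normal formula and 79.2% by noncentral t. At 30 per arm it is 83.4% by noncentral t.

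**Step 2. Carry SD 13 over to the two candidate analyses.** Assumptions that are not in the documents: SD 13 at baseline and at week 12, and a range of rho.
- Unadjusted change score: SD = 13 × √(2(1 − rho)), df = 52 at 27 per arm and 58 at 30.
- Linear model with arm, baseline SBP and two binary strata: residual SD = 13 × √(1 − rho²), df = 54 − 5 = 49 at 27 per arm and 60 − 5 = 55 at 30.

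Power by noncentral t, two-sided 0.05:

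| rho | SD of change | Change score, 27 per arm | Change score, 30 per arm | Residual SD | Adjusted model, 27 per arm | Adjusted model, 30 per arm |
|---|---|---|---|---|---|---|
| 0 | 18.4 | 50% | 54% | 13.0 | 79% | 83% |
| 0.2 | 16.4 | 59% | 64% | 12.7 | 81% | 85% |
| 0.3 | 15.4 | 65% | 70% | 12.4 | 83% | 87% |
| 0.4 | 14.2 | 72% | 76% | 11.9 | 86% | 89% |
| 0.5 | 13.0 | 79% | 83% | 11.3 | 89% | 92% |
| 0.6 | 11.6 | 87% | 91% | 10.4 | 93% | 95.5% |

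**Step 3. The rule as written lies between these.** One version was simulated: analyse change, and add baseline SBP only if it differs between arms at p < 0.05 (an assumed threshold, since the plan gives none). With 27 per arm and SD 13 at both times, power was about 66% at rho 0.3 and 80% at rho 0.5. With baseline SBP always in the model, simulation gave about 82% and 88%.

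**Step 4. How far the assumptions matter.**
- Unequal SDs: with a week-12 SD of 13, the SD of change equals 13 when SD_base² + 13² − 2 × rho × SD_base × 13 = 13², that is, rho = SD_base / 26. The break-even is 0.38 for a baseline SD of 10, 0.50 for 13 and 0.69 for 18.
- Week-12 SD not 13: if it were 16, the adjusted model at 27 per arm would give about 61% at rho 0 and 74% at rho 0.5.

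**The case against.** A reader might infer that section 9.2 contradicts 9.1 and 9.3. It does not. The 10 mm Hg is a between-arm effect, and under randomization the expected difference in week-12 level equals the expected difference in change. The outcome wording could even be read as the difference between arms at 3 months, although 9.1 says change. What is missing is the variance basis and the model.

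A reader might also infer that the trial is underpowered. The documents do not support that. The low figures need an unadjusted change score, which the plan never specifies, and a rho that it does not give. Baseline SBP is collected, and the wording of 9.3 allows it into the model. That objection stands as far as it goes, but being eligible for the model is not the same as being in it.

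The opposite overstatement is that putting baseline SBP in the model secures 80% whatever the correlation. That holds only if 13 is the SD of week-12 SBP, which 9.2 does not say.

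Finally, this is a pilot. It nevertheless states a formal hypothesis and an 80% power claim, and the remedy is small.

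**Conclusion.** The point holds as under-specification and should be fixed. Section 9.3 leaves the covariates of the primary analysis to observed differences, so neither baseline SBP nor the stratification factors are assured. Section 9.2 reproduces exactly, but for an unadjusted comparison with SD 13, and nothing links that SD to the reduction in SBP or to the model.

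No loss of power is proven. If SD is 13 at both times and rho is 0.2 to 0.5, the open choice spans 59 to 79% for an unadjusted change score and 81 to 89% for the adjusted model, at 27 evaluable per arm. The omission itself is certain. The size of its effect on power depends on the SDs and rho, which the sponsor would have to supply.

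**What to change.** **In 9.3**, for the primary outcome, replace the rule with a prespecified linear model (ANCOVA) of week-12 SBP on arm, baseline SBP and the stratification factors: network size (under 5, or 5 and more) and site as used in the randomization. Change in SBP may be kept as the response, because with baseline SBP in the model the treatment contrast is identical. Confirm that baseline SBP is the enrollment reading with the study cuff. Name any other covariates in advance or keep them to sensitivity analyses.

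**In 9.2**, have the sponsor confirm what 13 is (SD of the week-12 level, SD of change, or residual SD), its time point and source, and that alpha is two-sided. If it is the SD of week-12 SBP, state that it serves as a conservative residual SD for this model: about 79% power (t-based) with 27 evaluable per arm, and about 83% only if all 60 are evaluable. Otherwise, restate the power. If an unadjusted change score is kept, state the assumed SD of change or correlation.

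**Cost:** wording only. The enrollment reading and both stratification factors are already collected, no patients are added, and the strata terms cost about 0.1 percentage point of power.

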9.3 Statistical analysis

The primary outcome will be absolute reduction in systolic blood pressure at 3 months. Secondary outcomes will be attainment of a post-stroke hypertension treatment goal of <130/80 and patient-reported physical function (based on the NIH PROMIS physical function sub-scale). These outcomes will be evaluated, for intervention and control patients, on a 10-minute Zoom exit interview with direct observation on video by the study nurse.

Analysis will be conducted using intention-to-treat principles. Evaluation of the primary outcome and physical function secondary outcome will be completed using linear controlling for any differences in baseline variables despite randomization. Logistic regression will be used for attainment of post-stroke hypertension treatment goal of <130/80 controlling for any differences in baseline variables.

For Aim 2, we will assess how a subset of questions in PERSNET predict the set of network members who were engaged in the intervention. We will calculate positive predictive value of the subset questions versus full network survey questions.

10. Monitoring and Quality Assurance

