6.3 Counseling Sessions

All counseling sessions will take place remotely through Zoom, an MGB-approved secure video platform. In both the individual counseling and social network arm, participants will meet with the study nurse with an RA present on weeks 2,6, and 12 (+/- 7 days).

6.3a Counseling Session 1—On Week 2 (+/- 7 days)

The first counseling session will take place two weeks after initial enrollment. Study staff will ensure that only participants who have completed the consent process join the Zoom meeting.

Individual Counseling Arm

Patients in the individual counseling arm will meet individually with the study nurse. The nurse will provide counseling on the basics of blood pressure, taking and adjusting medications, monitoring blood pressure, reducing salt, and being physically active. The patients will then schedule their next session and collect a blood pressure measurement with cuff provided by the study staff under direct supervision by the nurse.

Social Network Arm

At the beginning of this session, the Research Assistant/study staff will confirm that all network-participants have completed the electronic consent process via REDCap.

The study nurse will begin the team-based counseling session in which she will provide counseling on teamwork and the same blood pressure control topics covered with the individual counseling group. The teamwork specific topics will include how networks can work together as a team, communication tips for engaging with one another and spreading positive messages and establishing the roles and responsibilities of each network team member. The team will schedule the following session and the patient will collect a blood pressure measurement with the cuff provided by the study staff under direct supervision by the nurse.

6.3b Counseling Session 2—On Week 6 (+/- 7 days)

The second counseling session will take place six weeks after initial enrollment. Participants in both arms will have received text messages every week in the three weeks between session 1 and session 2. Study staff will ensure that only participants who have completed the consent process join the Zoom meeting.

Individual Counseling Arm

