Patients in the individual counseling arm will again meet individually with the study nurse who will review information about taking and adjusting medications, monitoring blood pressure, reducing salt, and being physically active. The patients will also collect a blood pressure measurement with cuff provided by the study staff under direct supervision by the study nurse.

Social Network Arm

Patients in the social network arm will again meet with their network members and the study nurse to review information about teamwork in the context of taking and adjusting medications, monitoring blood pressure, reducing salt, and being physically active that were covered in session 1. The nurse will work with the team for a revised plan, if necessary, to achieve optimal blood pressure by the final session. The patients will also collect a blood pressure measurement with cuff provided by the study staff under direct supervision by the study nurse.

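### Section 9.3 leaves the covariates to observed imbalance, gives no handling for a missing week-12 SBP and no use for the supervised week-2 and week-6 readings; pre-specifying a model that uses them is a cheap, low-severity improvement

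*Combined protocol and SAP*

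**What the plan says.** Section 9.3 states the population as "Analysis will be conducted using intention-to-treat principles" and the primary model as "Evaluation of the primary outcome and physical function secondary outcome will be completed using linear controlling for any differences in baseline variables despite randomization". The noun after the word linear is missing. The outcomes are evaluated "on a 10-minute Zoom exit interview with direct observation on video by the study nurse", which is the week-12 visit. The goal-attainment outcome rests on the same reading: "Logistic regression will be used for attainment of post-stroke hypertension treatment goal of <130/80 controlling for any differences in baseline variables".

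Section 9.1 words the null hypothesis as "rates of systolic blood pressure change at 3 months will be equal in the intervention arm", but no slope or longitudinal model follows. Section 9.2 anticipates loss without stating a rate: "planned enrollment of 60 should be sufficient power for this study to allow for loss to follow-up".

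Section 6.3 has both arms measure SBP twice before the end line. At week 2 patients "collect a blood pressure measurement with cuff provided by the study staff under direct supervision by the nurse"; at week 6, "The patients will also collect a blood pressure measurement with cuff provided by the study staff under direct supervision by the study nurse". The Data Collection Schedule lists both readings in both arms. No section gives them a role in the analysis or says what happens when the week-12 reading is absent.

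**The concern.** Three choices that affect the primary estimate are open.

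- **Covariates.** Adjusting for whatever differs at baseline means the model is settled after the data are seen. Baseline SBP, the strongest natural covariate, and the strata (network size and hospital) enter only if they happen to be imbalanced.
- **Missing week-12 SBP.** An intention-to-treat analysis of a continuous outcome is undefined for patients without it until a rule is stated. A week-12 regression drops them by default.
- **Interim readings.** If patients leave because of their SBP, and do so differently by arm, dropping them biases the comparison. The week-2 and week-6 readings hold information to correct this.

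Arm-differential loss is plausible, though not shown. Section 6.4 places a group interview before the final BP in the network arm and not in the control arm. The direction of any bias depends on which arm and which patients leave, so it cannot be known in advance.

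**Working it through.** **Inputs from the documents.** SD 13, difference 10 mm Hg, alpha 0.05, power 80%, 54 needed and 60 enrolled (section 9.2); 1:1 allocation (section 5.1).

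**Assumed inputs.** Visit correlations and loss mechanisms are not in the documents. Write b for the baseline/post-baseline correlation (0.3 to 0.7) and r for the correlation between post-baseline visits (0.5 or 0.7).

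**1. The plan's own figure.** n per arm = 2 × (1.960 + 0.842)² × 13² / 10² = 26.5, so 27 per arm and 54 in total. This matches with a two-sided test. Implied loss = 1 − 54/60 = 10%. The planning SE at 27 per arm is 13 × √(2/27) = 3.54.

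**2. Bias under late, one-arm, SBP-driven loss.** Suppose that in one arm the odds of leaving after week 6 rise e-fold per SD of week-6 SBP, averaging 10%, while the other arm loses 10% at random. With z the week-6 SBP in SD units and p the loss probability, Cov(z, p) = E[p(1 − p)] = 0.0817. Mean week-6 SBP among those who stay therefore moves by 0.0817/0.90 = 0.091 SD, which is 0.091 × 13 = 1.18 mm Hg. To first order:

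- week-12 ANCOVA on baseline SBP is off by (r − b²) × 1.18;
- an unadjusted change score is off by (r − b) × 1.18.

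| b, r | ANCOVA off by | Change score off by | Simulated ANCOVA / longitudinal (truth 10) |
|---|---|---|---|
| 0.3, 0.5 | 0.48 | 0.24 | 9.49 / 9.97 |
| 0.3, 0.7 | 0.72 | 0.47 | 9.33 / 10.06 |
| 0.5, 0.5 | 0.30 | 0 | 9.72 / 10.02 |
| 0.5, 0.7 | 0.53 | 0.24 | 9.50 / 10.04 |
| 0.7, 0.7 | 0.25 | 0 | 9.75 / 10.01 |

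The last column is for control-arm patients with high SBP leaving (600,000 patients per scenario). The sign reverses if they leave the intervention arm. The longitudinal estimate (maximum likelihood using weeks 2 and 6) stays within 0.1 of 10. At 20% loss, a stress case not taken from the plan, the simulated ANCOVA gap is 0.48 to 1.42.

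**3. What that does to inference.** With 30 enrolled per arm the ANCOVA SE is 2.5 to 3.7 across the settings run. Under step 2 at 10% loss, ANCOVA 95% intervals cover 94.2 to 95.5%, and the longitudinal RMSE is 0.9 to 4.5% lower.

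**4. Where the gain shrinks (10% loss).**

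- Random loss, or equal dependence on SBP in both arms: the two analyses agree within 0.03.
- Half of the loss before week 2: gap 0.13 to 0.39. All of it before week 2: zero.
- Control-arm loss driven by the unseen week-12 value (MNAR): ANCOVA 8.9 to 9.4, longitudinal 9.2 to 9.5, so correction is partial. A 10 mm Hg shift in one arm's unseen values moves the contrast by 10 × 0.10 = 1.0.

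**5. Power.** With 27 complete cases per arm, power is 80.7%. If the interim readings explain 25 to 64% of week-12 variance (assumed), it is 81.7 to 83.2%, a gain of 1.0 to 2.5 points.

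**6. Baseline adjustment.** The SE is 3.54 × √(1 − b²) for ANCOVA and 3.54 × √(2(1 − b)) for an unadjusted change score, so the ratio is √(2/(1 + b)).

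| b | ANCOVA SE | Change-score SE | Ratio |
|---|---|---|---|
| 0.3 | 3.38 | 4.19 | 1.24 |
| 0.5 | 3.06 | 3.54 | 1.15 |
| 0.7 | 2.53 | 2.74 | 1.08 |

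**7. Goal attainment (systolic part only, unadjusted, 10% loss).** Week-12 means of 150 and 140 with SD 13 give 6.2% and 22.1% below 130, a difference of 15.9 points. Under step 2 with high-SBP patients leaving, complete cases give 15.3 to 15.7 (control-arm loss) or 17.0 to 17.5 (intervention-arm loss). Imputation from weeks 2 and 6 gives 15.8 to 16.0.

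**The case against.** The strongest reply is that this is a pilot, the bias rests on an assumed mechanism, and at the implied 10% loss it hardly affects coverage. That stands, and it sets the severity low. It is also true that the comparator is not the written plan: section 9.3 does not name week-12 ANCOVA, and an unadjusted change score would be off by only 0 to 0.5 mm Hg in the same scenario. That form, however, pays the precision cost in step 6. Reminders, back-up email (section 6.2), a final-session payment (section 6.6) and outreach to withdrawn participants (Implementation evaluation) may limit or explain loss, but they do not supply an analysis rule. The simulations used monotone loss and omitted the strata; intermittent missed visits were not examined.

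Three stronger readings are tempting and not supported.

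- A reader might infer that a longitudinal analysis is ruled out. The missing noun and the wording of section 9.1 leave it open; the exit-interview sentence only makes a week-12 regression likelier.
- A reader might infer that the baseline SBP itself is undefined, because section 6.1 also takes a discharge reading from the EHR. But section 6.1 calls only the enrolment study-cuff reading baseline, and the Baseline row of the schedule lists one supervised BP.
- A reader might infer that the result will be biased or the trial underpowered. The documents give no loss by arm, reasons or correlations, and 54 reproduces.

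**Conclusion.** The gap is real and of low severity. Section 9.3 fixes neither the covariates nor the handling of a missing week-12 SBP, and leaves supervised interim readings unused. If loss is late, in one arm and driven by SBP, week-12 ANCOVA is off by about 0.25 to 0.75 mm Hg at 10% loss, in either direction, which is small against its SE and would rarely change a conclusion. The gain is about zero under random or equally dependent loss, nil for patients lost before week 2, and partial under MNAR. The 8 to 24% larger SE of an unadjusted change score does not depend on any loss mechanism, only on the assumed correlation of 0.7 to 0.3. The case for change is that protection and pre-specification cost almost nothing; neither the trial nor its sample size is invalidated.

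**What to change.** Complete the model sentence in section 9.3 and pre-specify:

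- a repeated-measures model of SBP at weeks 2, 6 and 12 with arm-by-visit and baseline SBP-by-visit terms, unstructured visit covariance and a small-sample degrees-of-freedom correction; a week-12 ANCOVA with multiple imputation from weeks 2 and 6 is an acceptable alternative;
- the enrolment study-cuff reading as baseline SBP, and the randomisation strata as actually used;
- patients analysed as randomised, with the week-12 contrast as the primary estimate under a stated MAR assumption;
- imbalance-driven adjustment and a simple delta (MNAR) analysis as sensitivity analyses;
- the same imputation of week-12 BP for the <130/80 outcome;
- a report of missing readings by arm and visit, including patients with no post-baseline reading, whose missing values this model cannot recover.

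The cost is a few sentences and slightly more programming, with no new visits or data. The repeated-measures form adds a covariance assumption across three visits in 60 patients. Its SE was 0.6 to 2.2% smaller than ANCOVA under random loss at 10%, and 0.5% larger in one extreme case (opposite dependence in the two arms, all correlations 0.3).
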